Analysis plan for Aim 1: *Assess the validity and reliability of the Skyn monitor through comparison with laboratory grade breathalyzer in two fixed-dose lab alcohol administration sessions.* H1a. Threshold of detection. We define the threshold of detection as the consumption level with a 60% or higher detection rate. Rate of successful detection at the end of 1 beer, 2 beers, and 3 beers will be calculated respectively. This will be done by observing the data series and curves from the monitor readings.^{45,48} Successful detection of consumed alcohol is defined by a TAC peak (e.g., $\geq 0.02\text{g/dL}$) with a reasonably visible elevation slope for absorption (i.e., TAC curve goes up at a reasonable pace) and a declination slope for elimination (i.e., TAC curve goes down at the reasonable pace). H1b1. Relationship between TAC and number of drinks. The means of peak TAC readings and the areas under the curve will be calculated for 1, 2, and 3 drinks respectively. We expect a linear increase of peak TAC and area under the curve as number of drinks increase from 1 to 3. H1b2. Relationship between TAC and BrAC. We will examine the relationship between TAC and BrAC in three ways. First, a simple correlation will be calculated between recorded peak TAC and peak BrAC. A scatter plot will be produced to illustrate the bivariate correlation between these two readings. Second, the Bland-Altman method^{55,56} will be used to examine the magnitude of peak differences between TAC and BrAC. The average of paired TAC and BrAC peak values are plotted on x-axis, and the difference between them on y-axis. Stable TAC results across all BrAC levels will line up with a zero slope, which will suggest there is no systematic bias in estimating BrAC. Third, we will calculate the time-to-peak based on recorded TAC and BrAC readings. Their differences will be calculated to determine time delays in BrAC to TAC peaks. All these analyses will be conducted for TAC and BrAC readings obtained after each beer respectively. H1c: Two-week test-retest reliability. Pearson correlational coefficients will be calculated to indicate test-retest reliability using TAC peak /time-to-peak for each participant in two lab sessions. A correlation $\geq .7$ indicates good test-retest reliability.

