Analysis plan for Aim 2. *Validate Skyn monitor in daily life using a 2-week ecological momentary assessment (EMA), and evaluate its acceptability and usability for daily use.* H2a. Agreement between monitor and self-reports in EMA. Using the same definition of a successful detection and procedure of determining drinking episode in monitor data as in

H1a, we will calculate the detection rates by self-reported number of drinks. A receiver operating characteristic (ROC) curve will be plotted. H2b: Relationship between TAC and number of drinks. First, simple correlations will be calculated to examine the association between TAC (peak, AUC) and self-reported number of drinks using all drinking episodes. Second, a multilevel analysis will be used to examine the association between TAC (peak, and AUC) and number of drinks accounting for nested data within person. Acceptability and Usability. Ratings of the Skyn monitor will be summarized on aspects such as wearability, ease to operate, satisfaction with the product, and willingness to wear.

Analysis plan for Exploratory Aim. *Explore factors that may be associated with individual differences in monitor readings.* T-tests or Chi-square will be used to examine group differences (e.g., male vs. female, HIV+ vs. HIV-) in TAC parameters (i.e., peak, time-to-peak) and their relationships with # of drinks and BrAC.

Sample size and power. This is for how many participants need to complete the study. For Aim 1, the sample size was based on prior laboratory validation studies of transdermal alcohol monitors.^{36,45,57} Also, power analysis shows that a sample size of 40 will give us 80% power to detect a correlation $\geq .60$. For Aim 2, power analysis shows that $n = 40$ will give us 90% power ($\alpha = .05$) to detect an effect size $\geq .13$ in a multilevel analysis with $r = .60$ between measures.^{58,59} For Exploratory Aim, $n = 20$ in each group can give us 80% power to detect a large difference ($d \geq .80$).

7. Possible Discomforts and Risks:

Potential risks in this study include:

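### A zero Bland-Altman slope is read as absence of systematic bias, but the slope cannot detect a constant offset between TAC and BrAC

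*Combined protocol and SAP*

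**What the plan says.** Section 6 (Research Plan), Analysis plan for Aim 1, item H1b2, sets out three comparisons of TAC with BrAC.

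- Correlation: "a simple correlation will be calculated between recorded peak TAC and peak BrAC", with a scatter plot.
- Bland-Altman, which "will be used to examine the magnitude of peak differences between TAC and BrAC". The axes are the usual ones: "The average of paired TAC and BrAC peak values are plotted on x-axis, and the difference between them on y-axis". The plan then says that results stable over the range of BrAC "will line up with a zero slope, which will suggest there is no systematic bias in estimating BrAC".
- Time-to-peak for each measure, and the delay between them.

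The set is repeated by drink: "All these analyses will be conducted for TAC and BrAC readings obtained after each beer respectively". The plan does not name the mean difference, its confidence interval, limits of agreement or an acceptable size of difference.

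**The concern.** In a Bland-Altman plot, fixed bias is the height of the points above or below zero, and the slope shows whether the difference changes with level. The plan attaches its conclusion about systematic bias to the slope alone. A flat band of points lying well below zero satisfies the rule, although such a monitor underestimates BrAC in everyone.

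The other two comparisons do not fill the gap. A correlation is unaffected by a constant offset, and time-to-peak says nothing about level. Aim 1 is to assess validity against a laboratory-grade breathalyzer, and this is the analysis from which the plan draws its statement about bias. Followed literally, after each beer, it could put an incorrect statement about bias into the report.

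**Working it through.** The plan gives no expected bias, margin, SD or slope test, so there is no figure of its own to reproduce. The check is algebra, followed by an illustration.

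**Algebra.** Let T be peak TAC, B peak BrAC, D = T − B and A = (T + B)/2. Then

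slope of D on A = Cov(D, A)/Var(A) = [Var(T) − Var(B)] / [2 Var(A)].

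Replace T by T + c. All variances are unchanged, so the slope is unchanged, while the mean of D moves by exactly c. In the error-free case T = B + c, with c = −0.01, −0.02 or +0.02 g/dL, the slope is 0 and the mean difference is c. The slope is zero whenever the two variances are equal, even for unrelated readings.

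**Inputs to the illustration.**

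- From the documents: n = 40 (Sample size and power). The offset of 0.02 g/dL is scaled to the example detection level in H1a.
- Assumed: BrAC mean 0.05 and SD 0.012 g/dL, a two-sided 5% test of the slope, and a paired t test of the mean difference. There were 40,000 simulated trials per scenario.

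**(1) Equal variances, TAC 0.02 g/dL too low.** For r = 0.6, 0.7, 0.8, 0.9 and 0.95 the slope flags 5.1%, 5.0%, 5.0%, 4.9% and 4.9% of trials, which is its assumed error rate. The mean difference flags 100% throughout. For smaller offsets the slope stays at about 5%, and the mean difference performs as follows:

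| Offset (g/dL) | Flagged, r = 0.9 | Flagged, r = 0.6 |
|---|---|---|
| −0.01 | over 99.9% | over 99.9% |
| −0.005 | over 99.9% | 82% |

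**(2) Random error in TAC only.** With error SD e added to TAC, Var(T) − Var(B) = e² and Var(A) = 0.012² + e²/4, so the slope is e²/[2(0.012² + e²/4)]. For e = 0.012 this is 1/(2 × 1.25) = 0.40, with or without an offset.

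| e (g/dL) | Expected slope | Slope flagged, offset −0.02 | Slope flagged, offset 0 |
|---|---|---|---|
| 0.003 | 0.03 | 11.8% | 11.8% |
| 0.006 | 0.12 | 33.1% | 33.4% |
| 0.009 | 0.25 | 61.9% | 61.8% |
| 0.012 | 0.40 | 84.2% | 84.3% |

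The last two columns agree to within simulation error, so the slope carries no information about the offset. The mean difference flags 100% with the offset and about 5% without it.

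**(3) Unequal SDs, TAC 0.02 g/dL too low.** At TAC/BrAC SD ratios of 0.8, 0.9, 1.1 and 1.25, the slope flags 86%, 31%, 27% and 86% (r = 0.9), or 40%, 13%, 11% and 40% (r = 0.6). These flags come from the SD ratio, not the offset.

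**(4) A different error structure.** A separate simulation (5,000 trials per offset) put error of SD 0.006 in both devices, with a between-person SD of 0.012. For offsets of 0, −0.005, −0.01, −0.02, −0.03 and +0.02, the slope rejected in 4.5% to 5.4% of trials and the mean correlation stayed near 0.80. The mean difference rejected in 4.7% at offset 0, 95% at −0.005 and about 100% at the larger offsets.

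**(5) Precision of the mean difference.** With equal variances, the SD of D is 0.012 × √[2(1 − r)]: 0.0054 at r = 0.9 and 0.0107 at r = 0.6. The 95% CI half-width is 2.023 × SD/√40, which gives 0.0017 and 0.0034 g/dL.

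**The case against.** The strongest reply is that the sentence is about stability over BrAC levels, for which the slope is the relevant check, and that systematic bias is loose wording for level-dependent bias. The verb is also only a suggestion, with no formal test attached. Further, the plan names the Bland-Altman method and says it looks at the magnitude of differences. A constant offset would therefore show on the plot, and customary practice would report the mean difference. The scatter plot of peaks and the mean peak TAC values under H1b1 would also make a large offset hard to miss. H1b itself claims correlation, not absolute agreement.

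Much of this is fair and limits the severity. It does not supply a criterion for fixed bias. The conclusion as written is unqualified, and the one stated reading points to the slope. If only level-dependent bias was meant, the text should say so.

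Two limits on the illustration also stand. The rule can suggest bias in a monitor with none on average only when the variances differ. With equal error in both devices the slope test stays near 5%, as in (4). And the blind spot is an additive constant: proportional misreading does tilt the slope. For example, T = 0.8B gives (0.64 − 1)/(2 × 0.81) = −0.22.

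**Conclusion.** The concern holds. The stated reading of the plot is incorrect as an inference about systematic bias, because a zero slope is compatible with any constant offset. That result is algebraic and depends on none of the assumed values.

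The percentages do depend on the assumed mean, SDs, correlation and slope test, and on 40 participants with lab data. The Overview allows some participants to do the field test only, so the lab number could be smaller unless 40 complete the lab part. The BrAC level will also differ between one and three beers.

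This should be fixed, but it is contained: no hypothesis test and no sample size rests on the rule. What is at risk is the correctness of the report's statement about bias against BrAC.

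**What to change.** In H1b2, replace the zero-slope reading with the following:

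- Judge systematic bias by the mean TAC − BrAC peak difference with its 95% CI.
- Report 95% limits of agreement with their CIs, preferably against a tolerance set before analysis. The preset tolerance is good practice; its absence is not in itself the error.
- Describe the slope as a check for a difference that changes with level, read with caution because unequal error variances also tilt it.
- Apply the same reading to each per-beer analysis.

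Under the assumptions above, a CI half-width of about 0.002 to 0.003 g/dL means that n = 40 is enough to show an offset of 0.01 g/dL or more. The cost is one or two sentences in the analysis plan and minimal extra analysis of the same data, with no new procedures.

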Transdermal alcohol monitors can provide noninvasive, continuous monitoring of alcohol use by detecting ethanol diffused through the skin.^{27,31} Secure Continuous Remote Alcohol Monitor (SCRAM) anklet (Alcohol Monitoring Systems, Inc.) is the most widely used transdermal monitor but is designed to be used for law enforcement purposes.³² However, wider application of SCRAM anklet in clinical and intervention settings is limited by its shortcomings including its large size, high cost, and social stigma.^{20,25,29} The newest generation of wrist-worn alcohol monitor (BACtrack Skyn) is designed for consumer use and

addresses these limitations. The device looks like a fitness tracker, is inexpensive, samples up to every second, and transmits and shows data in real-time via a smartphone app. These advantages make this wrist-worn alcohol monitor a potentially ideal tool to be incorporated into smartphone-based intervention for alcohol use. However, prior to its application in research, thorough validation investigations of the monitor are needed. In this project, we will validate the Skyn monitor among 20 HIV+ drinkers and 20 HIV- drinkers (as comparison group) in both laboratory and field settings.

Fig.1. BACtrack Skyn Alcohol Monitor

5. Specific Aims:

Aim 1: Assess the validity and reliability of the Skyn monitor through comparison with laboratory grade breathalyzer in two fixed-dose lab alcohol administration sessions (Sec. 4.3, 4.5)

Hypothesis 1a: The monitor will be able to detect alcohol use at a low threshold (e.g., one drink).

Hypothesis 1b: The parameters of transdermal alcohol concentration (TAC) (e.g., peak, time-to-peak, area under the curve) will be correlated with number of drinks and breath alcohol concentration (BrAC).

Hypothesis 1c: The TAC readings in two lab sessions will show high correlation (test-retest reliability).

Aim 2: Validate Skyn monitor in daily life using a 2-week ecological momentary assessment (EMA), and evaluate its acceptability and usability for daily alcohol monitoring (Sec.4.4)

Hypothesis 2a: The monitor detected drinking episodes will correspond with self-reports in EMA.

Hypothesis 2b: The TAC readings will correlate with number of drinks in each drinking episode.

Exploratory Aim: Explore factors (e.g., gender, HIV status) that may be associated with individual differences in monitor readings (e.g., peak, time-to-peak, correlation with consumption level).

6. Research Plan:

Overview

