practice with the apps and monitor until they feel efficient with all. Further, participants may also be asked to wear the Secure Continuous Remote Alcohol Monitor (SCRAM; Alcohol Monitoring Systems, Inc.) anklet for the duration of the drinking session. The SCRAM anklet is similar to the Skyn device although it is worn around the ankle rather than the wrist. The SCRAM anklet will be used to evaluate whether transdermal alcohol concentration (TAC) readings obtained from each device converge, given that the SCRAM anklet is a validated TAC monitor. The SCRAM anklet has been approved and risk assessed in our previous study ([IRB201700623](#)).

Once practice with apps and monitor is completed, vital signs (including blood pressure, pulse, height and weight) will be collected, urine drug and pregnancy screening will occur, and participants will be provided a light snack (150-200 calories). Next, participants will be asked to complete some questionnaires (e.g., Alcohol Urge Questionnaire (AUQ); Positive and Negative Affect Scale (PANAS); Alcohol Purchase Task (APT); real time impaired control scale (ICRT); and a single-item question asking how much one wants alcohol currently).

Next, the drinking session will begin. We will provide several common beer brands with similar calorie (125-150) and alcohol level (~4.5% ABV) for the participants to choose from. Participants will be instructed to wear the Skyn monitor and SCRAM anklet and drink 3 beers by completing each beer in 15 minutes⁵⁰ with a 15-minute break in between (30min in total for each beer). During this time, the participant's BrAC will be measured every 30 minutes. Following the end of each beer during the 15-minute rest period, participants will also complete a brief packet of questionnaires very similar to the one they completed before drinking, plus the Biphasic Alcohol Effects Scale (BAES) and a single-item question asking how much one likes the effects of alcohol. Alcohol administration will be conducted per NIAAA guidelines⁵¹.

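### H1c judges two-week test-retest reliability by Pearson r ≥ .7 alone, which cannot show a session-to-session shift common to participants; report the paired session difference beside it

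*Combined protocol and SAP*

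**What the plan says.** Section 5 (Specific Aims, Aim 1) words the hypothesis as a correlation: "Hypothesis 1c: The TAC readings in two lab sessions will show high correlation (test-retest reliability"). Section 6 (Analysis plan for Aim 1, H1c) plans the matching statistic: "Pearson correlational coefficients will be calculated to indicate test-retest reliability using TAC peak /time-to-peak for each participant in two lab sessions". It adds that a correlation of .7 or more "indicates good test-retest reliability". No confidence interval for r is mentioned.

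The neighbouring analyses are these:

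- **H1a** (same section): "Successful detection of consumed alcohol is defined by a TAC peak", for which 0.02 g/dL is given as an example, together with visible rising and falling slopes. The plan then says: "We define the threshold of detection as the consumption level with a 60% or higher detection rate".
- **H1b2**: correlation, Bland-Altman and time-to-peak differences, all between TAC and BrAC. "All these analyses will be conducted for TAC and BrAC readings obtained after each beer respectively".
- **SCRAM** (Lab Session 1): "The SCRAM anklet will be used to evaluate whether transdermal alcohol concentration (TAC) readings obtained from each device converge". This compares devices, and wearing the anklet is optional.
- **H2a** (Analysis plan for Aim 2): applies the H1a definition of detection to the field data.

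Lab Session 2 repeats the Session 1 drinking procedure; only the training is replaced, by a survey. The sample-size paragraph plans for 40 completers, while the Overview lets some participants do the field test only.

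**The concern.** Good test-retest reliability is readily understood to mean that the monitor gives about the same reading for the same dose two weeks later. Pearson r addresses something narrower: whether participants keep their relative positions. If every Session 2 peak were lower by the same amount, or by the same proportion, r would be unchanged and H1c would pass. The same holds for time-to-peak if every participant's peak came later by the same interval. A change that differed between participants would lower r, so the blind spot is the common part only.

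For this monitor the common part matters. Detection depends partly on whether a TAC peak reaches a fixed cut, and that definition is carried into two weeks of field data collected between the two lab sessions. A reliability statement resting on r alone could be read as covering the stability of absolute readings when that had not been examined.

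**Working it through.** **1. The plan's own figure.** The only stated figure that covers the Aim 1 correlations is 80% power with 40 participants for a correlation of at least .60 (Sample size and power). The Fisher z formula, Φ(atanh(r)·√(n−3) − z), with n = 40, r = .60 and two-sided alpha .05 (assumed; the plan states alpha for Aim 2 only), gives Φ(0.693 × 6.083 − 1.960) = 98.8%. The stated 80% is therefore conservative. It concerns a test against zero correlation and has no bearing on session level, so the point does not depend on it.

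**2. Invariance.** For any a and any b > 0, corr(x, a + b·y) = corr(x, y). A 40-pair illustration with assumed mean 0.03 and SD 0.01 g/dL:

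| Session 2 peaks | r | Mean difference (95% CI), g/dL |
|---|---|---|
| as generated | .733 | +0.001 (−0.001 to 0.003) |
| all raised by 0.01 | .733 | +0.011 (0.009 to 0.013) |
| all multiplied by 0.6 | .733 | −0.010 (−0.012 to −0.008) |

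The paired difference reacts and r does not. The mean difference alone cannot tell an offset from a gain change; a plot of difference against average helps with that.

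**3. What each analysis would report under a common shift.** Inputs: 40 pairs (planned completers) and 20 pairs (an assumed lower case). The documents give no TAC mean, SD or reliability, so the shift is in SD units and the true correlation ρ is varied. Assumptions: bivariate normal, equal SDs, common shift 0.5 SD. The SD of the paired difference is √(2(1−ρ)). P(r ≥ .7) is by simulation; the chance that the CI excludes zero is from the noncentral t with noncentrality 0.5·√n / √(2(1−ρ)).

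| ρ | P(r ≥ .7), 40 pairs, with or without the shift | P(95% CI for difference excludes 0), 40 pairs | Both together |
|---|---|---|---|
| .60 | 15% | 93% | 15% |
| .70 | 52% | 98% | 52% |
| .80 | 93% | >99% | 93% |

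With 20 pairs and ρ = .80 the three figures are 86%, 92% and 80%.

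**4. What the added difference can resolve.** The 95% CI half-width is t × √(2(1−ρ)) / √n. At ρ = .80:

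- 40 pairs: 2.023 × 0.632 / 6.325 = 0.20 SD; smallest shift with 80% power 0.29 SD.
- 20 pairs: 2.093 × 0.632 / 4.472 = 0.30 SD; smallest shift with 80% power 0.42 SD.
- A shift of 0.25 SD has 68% power with 40 pairs and 39% with 20.
- Limits of agreement lie at the mean difference ± 1.96 × 0.632 = ± 1.24 SD.

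**5. Precision of r.** An observed r of exactly .70 has a Fisher z 95% CI of .50 to .83 with 40 pairs and .37 to .87 with 20. The criterion is met by the point estimate alone, so the interval should be shown.

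**The case against.** The strongest reply is that the plan does what it says: Hypothesis 1c predicts a high correlation, and a correlation is calculated. That stands. No planned estimate is biased and no stated hypothesis is mis-tested, which is why r and the .7 criterion should stay. The gap lies in the wider label attached to r.

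A second reply is that a shift might show elsewhere. A reader might infer that nothing in the plan could reveal one. The documents do not support that: they do not say whether the H1a detection rates, H1b1 means or H1b2 comparisons are pooled or shown by session. If shown by session, a common shift in TAC peak could be seen there. What can be said is that no comparison between sessions is committed to.

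A reader might also infer that a shift would carry the monitor across the 60% detection rule. For example, with normal peaks and detection judged on the peak alone, a 0.5 SD fall takes 70% to 51%. This does not follow from the documents. The 0.02 g/dL cut is only an example, detection also needs visible slopes, and the rule is not said to apply by session. Pooled, the same example gives (70 + 51)/2 = 60.5%, which still meets the rule.

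Finally, the size is illustrative. That r passes equally often with and without a shift is algebra; how often it passes depends on the assumed correlation, and falls to 15% at .60. This limits the size that can be claimed but leaves the blind spot in place.

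**Conclusion.** The point holds as a gap in the reporting plan that is cheap to close. Pearson r ≥ .7 answers Hypothesis 1c as worded and supports a statement about consistent ranking of participants. It does not support a statement that absolute TAC readings are stable over two weeks, and the plan commits to no analysis that would.

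The invariance is exact and needs no assumption. The percentages rest on normality, equal SDs, a 0.5 SD common shift and an assumed correlation; they show what could go unreported, not what will happen in this trial. It would be wrong to infer that the monitor drifts: the documents do not say so. A session difference, if found, would not by itself identify the sensor as the cause, since absorption or choice of beer could differ between sessions.

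**What to change.** In the H1c paragraph:

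- Keep Pearson r and the .7 criterion, and report r with its 95% CI.
- For TAC peak and time-to-peak, add the mean Session 2 minus Session 1 difference with 95% CI and Bland-Altman limits of agreement, with the plot of difference against average. This extends a method already planned in H1b2.
- Show the Session 2 minus Session 1 difference in BrAC peak alongside, to help separate a change in the sensor from a change in alcohol exposure. BrAC time-to-peak is a coarser companion, because during drinking "BrAC will be measured every 30 minutes" and afterwards about every 15 minutes.
- State that r alone supports consistency of ranking, and that any statement on absolute readings will be made in light of the session difference.

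The cost is two or three sentences and a little more analysis on data already to be collected in both sessions. The reliability statement may become less favourable. At a correlation of .80, shifts below about 0.3 SD may be missed with 40 pairs, and below about 0.4 SD with 20.

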This study will include two parts: laboratory and field validation of the Skyn monitor (Fig. 2). We will need complete data from 20 HIV+ drinkers (~50% male) and 20 HIV- drinkers (~50% male), but we will screen to 160 participants to account for potential screen failure and drop out. Participants will be invited to complete all components of the study or only the field test portion given the COVID pandemic. The PI will decide who will complete all components and who will complete only the field testing. Participants will first complete an alcohol administration session (Lab Session 1) at the simulated bar lab, where they will consume 3 standard drinks (i.e., 3 12oz beers) at a determined consumption rate (30min). The transdermal alcohol concentration (TAC) readings collected from the Skyn monitor will be compared with breath alcohol concentration (BrAC) and may be compared with the Secure Continuous Remote Alcohol Monitor (SCRAM; Alcohol Monitoring Systems, Inc.) anklet. After completing Lab Session 1, during a two-week field test, participants will use the Skyn monitor and record drinking episodes using an EMA app. After the field test, participants will return to the bar lab to complete a second alcohol administration session using the same procedures as in Lab Session 1 to obtain test-retest reliability of the monitor. They will also complete a questionnaire on the acceptability and usability based on their experience with the Skyn monitor and its smartphone app.

Of note, BACtrack Skyn monitor has been approved in our previous study ([IRB201700455](#) for laboratory alcohol administration study where participants wear the monitor while they self-administer alcohol in the bar lab).

[figure not shown]

Figure 2. Study Procedures

Participants

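### The HIV+ vs HIV- comparison of TAC parameters is a one-factor t-test; putting sex in the model would protect it against an uneven sex mix and, if sex affects TAC, make it somewhat more precise

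*Combined protocol and SAP*

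**What the plan says.** The Overview in section 6 sets the completer target: "We will need complete data from 20 HIV+ drinkers (~50% male) and 20 HIV- drinkers (~50% male". The sex figure is approximate, and no quota, blocking or stratified enrolment by sex is described.

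Section 5 words the Exploratory Aim as follows: "Explore factors (e.g., gender, HIV status) that may be associated with individual differences in monitor readings". Its analysis plan in section 6 reads: "T-tests or Chi-square will be used to examine group differences (e.g., male vs. female, HIV+ vs. HIV-) in TAC parameters". The parameters it lists are peak and time-to-peak, and the same sentence also covers their relationships with number of drinks and BrAC. The two contrasts are given as separate examples.

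No adjusted, stratified or two-factor model is named for this aim. The multilevel model in the Aim 2 analysis plan relates TAC to number of drinks. The Screening text says that baseline survey data will be used to explore variation between people in TAC, but gives no method.

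The sample size paragraph says of this aim that n = 20 "in each group can give us 80% power to detect a large difference", with d of .80 or more. Alpha is stated only for Aim 2, and sidedness is not stated.

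**The concern.** In the lab everyone receives the same three beers, not scaled to sex or weight, and the plan itself lists gender among the factors that may move the readings. If it does, a t-test of HIV+ against HIV- that ignores sex suffers in one of two ways:

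- **Sex mix equal in the two groups.** The HIV difference is estimated without bias, but the male-female spread is counted as noise. The interval is wider than it need be and the test is conservative.
- **Sex mix unequal.** Part of the sex difference appears as an HIV difference. Some drift is plausible. The Participants text describes an HIV+ source registry that is 60% male, and HIV- drinkers come partly by referral, with no rule on sex.

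At stake is the precision, and to a lesser degree the interpretation, of an exploratory contrast with 20 people per group. Aims 1 and 2 are not affected.

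**Working it through.** **Inputs.** From the documents: 20 per group, about half male in each, HIV difference d = .80. Assumed: alpha .05 (stated only for Aim 2), both one- and two-sided, and the sex difference d_s in units of the within-sex SD. The documents give no value for d_s, so a range is shown.

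**The plan's own figure.** Two-sample t-test, df = 38, noncentrality .80 × √(20/2) = 2.53. Power is 79.9% one-sided and 69.3% two-sided. The stated 80% therefore reproduces only one-sided.

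**With sex in the model.** With half men in each group, sex accounts for a share R² = (d_s²/4)/(1 + d_s²/4) of the variance within an HIV group. Removing it raises the standardised HIV effect to .80 × √(1 + d_s²/4), tested on df = 37. At d_s = .8:

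- R² = .16/1.16 = .138
- effect = .80 × √1.16 = .862
- noncentrality = .862 × 3.162 = 2.72
- power = 75.6% two-sided

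**Like-for-like comparison.** The textbook 69.3% is not the right baseline once the groups are exactly balanced. Balance removes sex from the actual variability of the HIV difference, while the t-test's standard error still contains it, so the plain test's power rises slightly above 69.3%. I therefore simulated the plain t-test with 10 men and 10 women per group (400,000 runs per row). Two-sided results:

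| Sex difference d_s | R² | Plain t-test | With sex in model | Gain (points) |
|---|---|---|---|---|
| 0 | 0 | 69.3% | 69.3% | 0 |
| .3 | .022 | 69.5% | 70.2% | about 1 |
| .5 | .059 | 69.8% | 71.9% | about 2 |
| .8 | .138 | 70.4% | 75.6% | about 5 |
| 1.0 | .200 | 70.9% | 78.7% | about 8 |

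The adjusted column and the first row come from the noncentral t; simulation of the adjusted model agrees. One-sided at d_s = .8, the gain is about 3 points (81.4% to 84.8%).

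**Interval width.** The residual SD shrinks by 1/√(1 + d_s²/4), ignoring the lost degree of freedom. That is .970 at d_s = .5, .928 at .8 and .894 at 1.0, so intervals are about 3%, 7% and 11% narrower.

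**False positives at d_s = .8, no HIV difference, nominal 5% two-sided.**

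- Exact 10/10 balance: about 3.4% for the plain t-test.
- 12 men in one group and 8 in the other: about 5.7% for the plain t-test. The bias in the HIV difference is (12 − 8)/20 × .8 = .16 within-sex SD.
- The adjusted model: about 5% in both cases.

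**The case against.** The strongest reply is that this is an optional refinement and not an error. Much of that stands. The HIV contrast is an example within an aim labelled exploratory, not a stated hypothesis. Under balance the plain t-test is unbiased and errs on the cautious side. The size of the gain rests wholly on an assumed sex effect, since the plan says only that gender may matter. The d = .80 row borrows the plan's detectable difference, which is not an expected sex effect. The fixed-dose argument bears on lab peak TAC; it is weaker for time-to-peak and does not carry over to field readings, where the dose is not fixed. Sex is also not the only candidate: height and weight are recorded too.

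A reader might infer three stronger things that the documents do not support:

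- **That sex is a design stratum which the analysis is bound to respect.** The text gives only an approximate recruitment target.
- **That the sex balance goes unused.** The plan's own male vs. female comparison uses it.
- **That adjustment lifts power from 69% to 76%.** This sets a textbook unadjusted figure against a balanced adjusted one. Like for like, the gain at d_s = .8 is about 5 points.

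What the reply does not remove is that the variable is already collected, the plan suspects that it matters, and one model guards against both the loss of precision and drift in the sex mix at almost no cost.

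**Conclusion.** The point holds as a minor one. The planned HIV comparison ignores a recorded factor that the plan itself thinks may affect the readings. If sex has an effect, the plain t-test loses some precision when the groups are balanced and is mildly confounded when they are not. In power terms the gain from adjustment runs from nothing at d_s = 0 to about 8 points at d_s = 1.0. It reaches about 5 points only if the sexes differ by roughly .8 within-sex SD.

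These figures assume 10 men and 10 women per group, normal errors with equal variance, alpha .05 two-sided, an HIV difference of d = .80 and no sex-by-HIV interaction.

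The gap between the stated 80% and the two-sided 69.3% should not be put down to the missing adjustment. It comes from sidedness, which is a separate matter.

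**What to change.** In the analysis plan for the Exploratory Aim, state that for each continuous TAC parameter (peak, time-to-peak) one linear model with HIV status and sex will be fitted, that both adjusted differences will be reported with 95% confidence intervals, and that the t-tests will be kept as descriptive companions. Report the number of men and women in each HIV group beside the results.

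The change takes a sentence or two and no new data. It uses one residual degree of freedom (37 instead of 38), which is negligible even if sex has no effect. The model assumes that the HIV difference is the same in men and women; with about 10 per cell that assumption can be looked at descriptively but hardly tested. The change does not cover the rest of the planned comparison, on relationships with number of drinks and BrAC.
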